7.7.3. Treatment outcomes

Primary objective 3:

The treatment outcomes will be assessed using time-to-event analysis, namely Kaplan-Meier fit or other relevant competing risk models. For each outcome, the time will be defined as follows (Figure 3):

- overall survival:
 - time from index until death (event) or end of study (censoring event)
 - when analysing by treatment lines, start the time from initiation of each treatment line
- progression free survival (PFS, defined using time to next treatment (TTNT) proxy):
 - time from initiation of the current treatment line until the initiation of the next treatment line (event), death (competing risk/event), or end of study (censoring event)

The Kaplan-Meier fits will be visualized, and the median survival/PFS of the patients will be reported as well, if reached.

Additionally, corresponding Cox proportional-hazards model will be fitted, including clinical variables as covariates (including but not limited to age, sex, IMDC risk score, diagnosis year, and treatment line number). The hazard ratios, 95% confidence intervals and p-values corresponding to each covariate will be reported.

[figure not shown]

Figure 3. Graphical illustration of definitions of treatment outcomes. Abbreviations: LOT = line of treatment.

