- Treatment initiation for mRCC (sunitinib, pazopanib, cabozantinib, ipilimumab, nivolumab)

When analyzing the treatment outcomes, index is defined as the date of the treatment initiation.

End of follow-up (whichever of the following occurs first):

- Death
- Moving outside of HDSF
 - Approximated using data of healthcare contacts; no contacts to specialty care of HDSF within 2 years (patient censored at the last recorded visit)
- End of study (31.12.2021)

Length of follow-up (in years): ('end of follow-up' – 'index' + 1)/365.25

Definitions for characteristics cohort

Index:

- For mRCC patients, same as for the mRCC cohort (i.e. approximated metastasis date)
- For RCC patients, the date of the first record of RCC diagnosis (ICD-10: C64)

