7.3. Variables

Source for all variables is the data lake of HDSF.

Table 2. List of study variables. Abbreviations: PO=primary objective, SO=secondary objective.

Variable	Role/Relevant objective	Operational definition
ICD-10 diagnoses; RCC diagnoses	Patient inclusion/exclusion IMDC risk category	yes/no
ICD-10 diagnoses: co-diagnoses (e.g. renal insufficiency and hypertension)	PO1, SO1	yes/no; co-diagnoses before and after index
Date of birth	Patient inclusion PO1	Date; age defined at index based on birth date
Date of death	End of follow-up PO3	Date
Gender	PO1	Female/male
Home municipality	Patient inclusion End of follow-up	Home municipality at each healthcare contact
Weight	PO1	kg
Height	PO1	m
Body mass index (BMI)	PO1	derived from weight and height
Smoking status (if available in structured format)	PO1	yes/no
Outpatient visits (including emergency room visits)	Patient inclusion and index definition (visits to oncologist) SO2	Date, physician's specialty, type of arrival
Hospitalizations	SO2	Start and end dates
Procedures and operations (including nephrectomy)	PO1 SO1 SO2	Procedure code, date
Medical imaging	SO1 SO2	Imaging code, date
Medications; including - hospital medications - prescriptions	Patient inclusion/exclusion and index definition PO2 PO3 SO1 SO2	Dates, ATC-codes, active substance
Laboratory testing	IMDC risk category PO1	Dates, test id, result
Zubrod/ECOG performance status	IMDC risk category PO1	scale 0-5; converted to Karnofsky
PAD histology (if available in structured format)	PO1	
Staging of RCC, the tumor-node-metastasis (TNM) classification	Patient inclusion and index definition PO1	scale 1-4 (stages)

PFIZER CONFIDENTIAL

Table 3. List of medications for RCC treatment. ATC= Anatomical Therapeutic Chemical.

	Active substance	Brand name	ATC-code at the moment in use	ATC-code previously in use
Oral medications	axitinib	Inlyta	L01EK01	L01XE17
	everolimus	Afinitor	L01EG02	L01XE10
	cabozantinib	Cabometyx	L01EX07	L01XE26
	pazopanib	Votrient	L01EX03	L01XE11
	sorafenib	Nexavar	L01EX02	L01XE05
	sunitinib	Sutent	L01EX01	L01XE04
Intravenous medications	ipilimumab	Yervoy	L01XC11	
	nivolumab	Opdivo	L01XC17	

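### Sections 7.2 and 7.7.3 give different censoring rules for OS and TTNT, and which rule misleads depends on whether deaths after move-out are captured, which the protocol does not say

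*Combined protocol and SAP*

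**What the plan says.** Section 7.2 (Setting), in the definitions for the mRCC cohort, sets one end of follow-up: "End of follow-up (whichever of the following occurs first"). The list holds death, moving outside HDSF, and "End of study (31.12.2021"). Moving is not observed directly. It is inferred from "no contacts to specialty care of HDSF within 2 years (patient censored at the last recorded visit"). The line just before this list resets the time origin for outcomes: "When analyzing the treatment outcomes, index is defined as the date of the treatment initiation". It does not exempt outcomes from the follow-up rule.

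Section 7.7.3 (Treatment outcomes) defines OS as "time from index until death (event) or end of study (censoring event"). The PFS proxy, TTNT, runs to "initiation of the next treatment line (event), death (competing risk/event), or end of study (censoring event"). Move-out appears in neither definition, and the section does not refer back to 7.2.

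On data, section 7.3 states "Source for all variables is the data lake of HDSF". Table 2 there lists date of death. It also gives home municipality a role in ending follow-up, defined as "Home municipality at each healthcare contact".

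**The concern.** OS and TTNT are primary objective 3 (section 6.1). Two programmers could each follow the protocol, code different censoring, and report different Kaplan-Meier curves, medians and Cox hazard ratios. Section 7.2 lists end of study separately from moving, so the words end of study in 7.7.3 do not, as they stand, include move-out.

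Each rule has a weakness, under opposite conditions:

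- **7.7.3, if later deaths are not captured.** A patient who leaves and dies elsewhere counts as alive to 31.12.2021. Survival is overstated.
- **7.2, if deaths are captured.** Censoring depends on what happens in the next two years. A death within two years of the last visit counts as an event. A patient who survives the two years is taken back to the last visit and loses that survival time. Survival is understated.

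Left open, the rule for a primary outcome could be settled after the data are seen.

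**Working it through.** **1. The plan's own figure.** The only planning number is cohort size (section 7.5): 1,100 × 0.20 = 220 and 1,100 × 0.50 = 550. It reproduces and does not depend on the censoring rule.

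**2. How backdating acts.** Take two patients whose last contact is at month 12.
- Patient A dies at month 30. The gap is 30 − 12 = 18 months, under two years, so 7.2 records a death at month 30.
- Patient B dies at month 40. The gap is 28 months, so 7.2 censors at month 12.

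If both deaths are known, A stays in the risk set as an event and B, who lived longer, is removed. The estimated hazard is too high.

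**3. Simulated size.** The documents give no move-out rate, contact pattern or death-capture rate, so every input here is an assumption:
- index dates uniform over the 12 years to 31.12.2021;
- exponential OS;
- contacts about every 3 months until move-out;
- constant yearly move-out;
- deaths after move-out either all recorded or none recorded.

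There were 300,000 simulated patients per scenario. Kaplan-Meier results at a true median of 24 months (true 5-year OS 17.7%):

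| Later deaths | Move-out per year | 7.7.3: median; 5-yr OS | 7.2: median; 5-yr OS | Difference |
|---|---|---|---|---|
| Not recorded | 2% | 24.6; 20.6% | 23.9; 17.7% | 0.7 mo; 2.9 pts |
| Not recorded | 5% | 25.6; 24.6% | 24.0; 17.9% | 1.6 mo; 6.7 pts |
| Not recorded | 10% | 27.6; 30.7% | 24.0; 18.1% | 3.6 mo; 12.6 pts |
| All recorded | 2% | 23.9; 17.7% | 23.6; 17.0% | 0.3 mo; 0.7 pts |
| All recorded | 5% | 24.0; 17.6% | 23.3; 16.1% | 0.7 mo; 1.5 pts |
| All recorded | 10% | 24.1; 17.5% | 22.7; 14.6% | 1.4 mo; 2.9 pts |

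In each scenario one rule is close to the truth and the other is not. Across true medians of 18-36 months and move-out of 2-10% per year, the difference in medians runs from 18.0 − 17.8 = 0.2 to 45.4 − 36.1 = 9.3 months. With no 2-year gaps the rules give identical results.

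**4. Against sampling error.** Ignoring censoring, the 95% half-width of a Kaplan-Meier median under exponential survival is 1.96 × m / (ln 2 × √n). For m = 24:
- n = 220: 47.04 / (0.693 × 14.83) = 4.6 months;
- n = 550: 47.04 / (0.693 × 23.45) = 2.9 months.

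For 5-year OS the binomial half-width is 1.96 × √(0.177 × 0.823 / n): 5.0 points at n = 220 and 3.2 at n = 550, and somewhat wider with staggered entry.

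**5. Calendar time.** A 2-year gap must be complete by 31.12.2021, so 7.2 cannot flag a patient whose last contact is after 31.12.2019.
- Later deaths not recorded: it flags 89-94% of movers indexed in 2010-2017, but 32-36% of those indexed in 2018-2021.
- All deaths recorded: 48-59% against 18-22%.

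The effect on medians is much smaller. At 2-5% per year and true medians of 24 or 36 months, the 7.2 medians for the two periods differ by at most about 1.2 months.

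**The case against.** The strongest reply is that 7.7.3 is shorthand. Section 7.2 defines follow-up for the whole mRCC cohort, nothing exempts outcomes from it, and Figure 3, which illustrates the outcome definitions, is not available to this review. This is a fair reading, and it would reduce the contradiction to a one-phrase edit. But the text does not say so, and that edit would make the 7.2 rule govern OS, which is the wrong choice if deaths are captured.

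Second, the study is mainly descriptive, no alpha or power depends on this, and the median shifts at 2-5% per year lie inside the sampling error shown above. That stands, and it limits the severity. It does not make the choice immaterial. Bias does not shrink with sample size, and the 6.7-point shift in 5-year OS exceeds the half-widths above, although it needs 5% yearly loss with every later death unseen. Section 7.7.3 names the median, not 5-year OS, as the summary to report. The analysed cohort will also be smaller than 220-550, because section 7.2.2 excludes untreated patients, so sampling error will be larger.

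Third, Table 2 may be meant to implement the move-out rule, since 7.2 relies on healthcare contacts and municipality is recorded at each contact. A reader might infer that municipality is collected and then ignored. The documents do not show that; they only fail to say how it enters the rule.

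**Conclusion.** Wrong as written: the two sections give contradictory censoring rules for primary outcomes. It should be fixed. The conflict rests on the text alone; its size rests on assumed rates. At 2-5% yearly move-out and a true median of 24 months the rules differ by about 0.3-1.6 months in the median and 1-7 points in 5-year OS.

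Four stronger readings are not supported:

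- **That survival will be biased in a known direction or amount.** The direction turns on death capture and the size on move-out. The documents state neither.
- **That upward and downward bias act together.** They need opposite assumptions, and in each case the other rule is close to the truth.
- **That comparisons over calendar time are seriously distorted.** Flagging is uneven by period, but the effect on medians is small at these rates.
- **That TTNT bias has been shown.** TTNT was not simulated. Under 7.7.3 a next line started outside HDSF could be missed if it does not reach the data lake, but the documents do not say whether it does.

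**What to change.** 1. Establish with the data holder, and state in the protocol, whether dates of death reach the data lake regardless of later HDSF contact, and whether treatment lines started elsewhere are visible.
2. Use one OS rule in both sections. If deaths are captured, follow OS to death or 31.12.2021 and do not apply the contact-gap rule to it. If they are not, replace end of study in 7.7.3 with the 7.2 end of follow-up.
3. Specify TTNT separately, because capturing deaths does not mean capturing next lines. Whatever the answer on deaths, state that patients are censored at the 7.2 end of follow-up when lines started outside HDSF are not visible.
4. Date move-out by home municipality where a contact shows it. Keep the 2-year gap as back-up, since a mover who never returns to HDSF has no such contact.
5. Report the other rule as a sensitivity analysis, with the number of patients censored for a contact gap.

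The cost is an enquiry to the data holder, amended wording and one extra run. Death date and home municipality are already collected.

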6.1. Primary objectives

1. Characterize patients with RCC and with advanced/metastatic RCC (treated and non-treated separately) including e.g. demographics and IMDC risk score.
2. Define treatment patterns and treatment sequences in mRCC.
3. Assess outcomes by treatment line and from diagnosis
 - a. Progression free survival (via proxies such as time-to-next treatment)
 - b. Overall survival
 - i. time to event analyses
 - ii. Cox models

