7.2.3. Patient stratification

Analyses will be stratified by:

- IMDC risk category (defined at the initiation of the first treatment for the metastatic RCC; see Table 1 and listing below for definitions)
 - Applied to all primary and secondary objectives
- Treatment line
 - Applied to primary objective 2 and 3

IMDC risk factors (each criterion accounts for +1 for the risk score):

1. Less than a year from time of initial RCC diagnosis to initiation of treatment for the metastatic RCC

2. Performance status* <80% (Karnofsky)
3. Hemoglobin* below normal (women < 117 g/l; men < 134 g/l)
4. Serum calcium* above normal (> 2.51 mmol/l)
5. Neutrophiles* above normal (> 6.3 x 10⁹/l)
6. Thrombocytes* above normal (> 350 x 10⁹/l)

** for performance status and laboratory values data of ± 3 months around the treatment initiation will be utilized due to possibly sparse data. If multiple records are available, the record closest to the treatment initiation will be utilized.*

Table 1. IMDC risk scores and categories based on two different approaches depending on the data coverage

	IMDC risk category	Total score of IMDC risk factors	Explanations/missing values
Option 1*	Favorable risk	0	no missing values allowed
	Intermediate risk	1-2	1) total score = 1; max 1 risk factor allowed to have missing value 2) total score = 2; no missing values allowed
	Poor risk	3 or more	max 3 risk factors allowed to have missing values
	Unknown risk**	-	when none of the above risk categories can be assigned
Option 2*	Appear favorable	0	all non-missing values for the risk factors indicate favorable risk max 3 risk factors allowed to have missing values
	At least intermediate	≥1	at least one risk factor criterion is met max 3 risk factors allowed to have missing values
	Poor	≥3	at least three risk factor criteria is met max 3 risk factors allowed to have missing values
	Unknown**	-	when none of the above risk categories can be assigned, i.e. more than 3 risk factors have missing value

** If small number of missing values is observed, the option 1 will be selected. If large number of missing values is observed and thus majority of patients were to belong to the “unknown” group of the option 1, the option 2 will be selected. The selection will be done after the data release and monitoring of data coverage.*

*** Patients with unknown risk category, will be analysed as own patient group.*

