7.7. Data analysis

Data will be analyzed using primarily descriptive measures, which include mean/median values for continuous variables and proportions for categorical variables. Costs will be estimated using data of visits, hospitalizations, procedures, etc. and utilizing publicly available price listings. For treatment outcomes, Kaplan-Meier estimates and/or corresponding time to event competing risk models will be utilized.

All analyses will be reported for the whole advanced/metastatic RCC patient population and stratified by the IMDC risk score. Additionally, treatment patterns and treatment outcomes will be reported by treatment lines.

Analyses are based on structured data, with the exception for potential text-mining of IMDC risk score or its components.

Due to the retrospective nature of the study, missing and/or incomplete data is expected in some of the medical records. Patients' records will not be excluded because of missing values, and missing data will not be imputed, i.e. the data will be analyzed as they are recorded in the electronic medical records. The proportion of missing values per variable will be reported.

Analyses will be performed using R, a language and environment for statistical computing, in Rstudio-server environment.

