7.7.5. Healthcare resource utilization

Secondary objective 2:

Healthcare resource utilization (HCRU) will be defined as number of outpatient clinic visits, ER visits, hospitalizations, hospital inpatient days, performed procedures, operations, imaging, and laboratory tests. The price will be evaluated for each entry using publicly available price listings.

The absolute number of each HCRU type and the absolute costs associated will be reported. Additionally, the estimates will be scaled to “per-patient” estimates (by dividing the absolute estimates with the number of contributing patients) and to “per patient year” estimates (by dividing the absolute estimates by the number of contributing patient years).

Additionally, assess the HCRU cumulatively over time, i.e. annual costs per patient during the first 5 years from index, each year separately (i.e., the costs during the first year after the diagnosis of advanced/metastatic RCC, during the second year, etc).

No statistical testing for difference between groups will be performed and estimates will be descriptive in nature. However 95% confidence intervals (CI) for the estimates will be derived using bootstrapping over patients.

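### The Cox model in 7.7.3 lists treatment line number but gives no row structure or patient-level variance; if OS rows are pooled over lines, CIs for patient-level covariates are too narrow

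*Combined protocol and SAP*

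**What the plan says.** Primary objective 3 in 6.1 reads "Assess outcomes by treatment line and from diagnosis", and Cox models are listed there under overall survival. Section 7.7.3 measures OS from index to death, censored at end of study, and adds: "when analysing by treatment lines, start the time from initiation of each treatment line". It then plans a Cox model to accompany the Kaplan-Meier fits, with clinical covariates "including but not limited to age, sex, IMDC risk score, diagnosis year, and treatment line number". On output it says: "The hazard ratios, 95% confidence intervals and p-values corresponding to each covariate will be reported".

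Other sections bear on how this is to be read:
- Section 7.2.3 makes treatment line a stratification factor, "Applied to primary objective 2 and 3", and fixes the IMDC category once per patient, at the start of first treatment for metastatic disease.
- Section 7.7 says: "Additionally, treatment patterns and treatment outcomes will be reported by treatment lines".
- Section 7.2 sets the index for treatment outcomes at treatment initiation.
- Patient-level resampling appears only in 7.7.5, for healthcare resource use: "However 95% confidence intervals (CI) for the estimates will be derived using bootstrapping over patients".

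No section gives the row structure, time scale or variance estimator of the Cox model. Annex 1 lists no stand-alone documents. Figure 3, which illustrates the outcome definitions, is not shown in the copy reviewed and may clarify the time origins.

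**The concern.** Age, sex, IMDC category and diagnosis year are carried by the patient; line number changes within the patient. In a model for a single line, line number is constant and drops out. In an OS model with one baseline row per patient, it has no legitimate baseline value. So listing it implies either pooled patient-line rows or a time-dependent covariate. The plan defines the by-line clock that pooled rows would need and never mentions time-dependent covariates.

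On pooled OS rows, one death closes the survival time of every line that patient started. Ordinary Cox variance treats these as separate deaths, so the CIs for patient-level covariates shrink without any added information. This needs no unexplained heterogeneity between patients. At stake is the precision claimed for age, sex and diagnosis year in a primary objective. For IMDC, an established predictor, the issue is CI width rather than false positives. With the structure unstated, analysts could also choose after data release among readings that give different error bars.

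**Working it through.** **The plan's own figure.** Section 7.5 gives about 1,100 RCC patients, of whom 20-50% become metastatic: 1,100 x 0.20 = 220 and 1,100 x 0.50 = 550. This reproduces. The Cox models use only treated patients, a subset, so N = 120 was also examined. The plan gives no event count, power, alpha or target hazard ratio for the Cox model, and no number of lines per patient. Those inputs are assumptions.

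**Hand approximation.** Let a patient contribute m rows that share the covariate and the death. Model-based information grows with E[m], but the true variance of the score grows with E[m²]. So model-based SE / true SE is about √(E[m]/E[m²]). Assume at most three lines, chance p of each further line, and no censoring. Then P(1) = 1-p, P(2) = p(1-p), P(3) = p².
- p = 0.20: E[m] = 1.24, E[m²] = 1.80, ratio √0.689 = 0.83, about 17% too narrow.
- p = 0.35: E[m] = 1.47, E[m²] = 2.66, ratio √0.553 = 0.74, about 26%.
- p = 0.60: E[m] = 1.96, E[m²] = 4.60, ratio √0.426 = 0.65, about 35%.

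This treats a patient's rows as fully redundant, so it should lie near the upper end.

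**Simulations.** Both fit a null binary patient covariate plus line number to pooled OS rows.
- Simulation 1: N = 120 to 550, at most three lines, entry uniform over 144 months, p from 0.20 to 0.60, gamma frailty variance 0 or 0.5, and two data-generating models.
- Simulation 2: N = 220 and 550, at most four lines, death hazard 0.4 per year, uniform censoring at 0.5-10 years, line-switch rates 0.2, 0.5 and 1.0 per year, no frailty in the rows shown.

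| Rows per patient | Sim. 1: CI too narrow by | Sim. 1: type I error | Sim. 2: SE ratio (N=220, 550) | Sim. 2: coverage of 95% CI |
|---|---|---|---|---|
| about 1.2 | 12-17% | 8-11% | not run | not run |
| about 1.4 | 19-26% | 11-15% | 0.755, 0.769 | 86.9%, 85.5% |
| about 1.6-1.7 | 26-32% | 13-19% | not run | not run |
| about 1.8-1.9 | 30-35% | 17-21% | 0.647, 0.644 | 78.5%, 79.8% |

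An SE ratio of 0.644 means 1 - 0.644 = 36% too narrow. At N = 220 without frailty, simulation 1 gave model-based over empirical SEs of:
- 0.140/0.168 = 0.83 at 1.19 rows
- 0.130/0.164 = 0.79 at 1.40 rows
- 0.113/0.170 = 0.66 at 1.85 rows

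**With patient-clustered variance.** Coverage is 93-95% in simulation 2. Type I error in simulation 1 is 4-7% at N of 220 or more and 5-9% at N = 120. A patient bootstrap at N = 220 gave 4.0%, 6.0% and 4.4% for p = 0.20, 0.35 and 0.60. For a covariate with an assumed true hazard ratio of 2, coverage is 81-93% model-based and 92-95% clustered. Stratifying the baseline hazard by line without clustering does not help: type I error stays at 7-21%.

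**What is not affected.** One OS row per patient: coverage 94.3%. OS with line as a time-dependent covariate: type I error 4.0-6.5%. Pooled time-to-next-treatment rows: type I error 4-8% in simulation 1; coverage 96.5%, 92.4% and 93.1% at frailty variance 0, 0.5 and 1.0 in simulation 2. The CI for line number itself is not materially too narrow (SE ratio 0.92-1.35).

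**Line-number hazard ratio.** With line as a time-dependent covariate that has no true effect, its estimated hazard ratio was 0.99-1.01 without frailty but 1.46-1.53 with it. Selection of patients into later lines drives it, so it is descriptive only.

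**The case against.** The strongest reply is that the plan contains no demonstrated error. Sections 7.2.3 and 7.7 point towards separate analyses by line. The lead OS definition runs from index, and 7.2 places that index at treatment initiation, which allows one row per patient. The covariate list is open-ended, so line number need not enter every model. All this stands. A reader might infer that the plan commits to pooled rows with naive variance and will therefore report wrong intervals; the text does not support that.

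The reply does not remove the gap. Neither one-row-per-patient nor single-line models can validly use the line number that 7.7.3 lists. Counting the total lines ever received would make it fit one row per patient, but that puts future information into a baseline covariate. The result is immortal-time bias, which no variance correction repairs.

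Two further objections hold in part. The magnitudes show sensitivity to unknown inputs, not this study's own error rate. And 7.7 says "Data will be analyzed using primarily descriptive measures": no decision rests on a Cox p-value. That limits the consequence, but the plan still undertakes to report a 95% CI for each covariate, and it should have its stated meaning.

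**Conclusion.** The point holds conditionally. Section 7.7.3 leaves the Cox data structure and variance unstated while listing a covariate that needs either pooled patient-line rows or a time-dependent formulation. If OS rows are pooled with model-based variance, CIs for patient-level covariates are too narrow by roughly 12-17% at about 1.2 rows per patient, 19-26% at about 1.4 and 30-36% at about 1.8-1.9. A larger cohort does not cure it: N = 220 and N = 550 behave alike. The direction follows from counting one death several times; the size depends on assumed lines per patient, survival and censoring.

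It would be too strong to extend this to the plan's other outcome analyses. Time to next treatment is little affected, and per-line Kaplan-Meier estimates and one-row-per-patient OS models are not affected. It should be fixed before analysis, but it does not undermine the study.

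**What to change.** In 7.7.3, state the row structure and time scale of each Cox model and which outcomes include line number. For any OS model that pools lines, keep line number as a covariate and use patient-clustered robust variance, or a patient-level bootstrap as 7.7.5 already does for resource use. Acceptable alternatives are line-specific models without line number, or one OS model per patient with line as a time-dependent covariate. If the baseline hazard is instead stratified by line, clustering is still needed, and the plan should say that no line-number hazard ratio will be reported. Rule out total lines ever received as a baseline covariate, and describe any line-number hazard ratio as descriptive.

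The cost is one or two sentences and a cluster term in the R call, with no new data. CIs for patient-level covariates in pooled OS models will be wider. At N = 220, clustered over model-based SE is 0.158/0.140 = 1.13, 0.164/0.130 = 1.26 and 0.165/0.113 = 1.46, so about 13%, 26% and 46% wider at 1.2, 1.4 and 1.85 rows per patient. Line-specific models avoid clustering but leave few patients late on: with N = 220 and a 35% chance of each further line, at most 220 x 0.35² = about 27 reach line 3.

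Two minor, separate points:
- Section 7.7.1 names a t-test for differences between strata. Keep it for two-group contrasts, and use one-way (Welch) ANOVA when more than two IMDC strata are compared.
- If Table 1 Option 2 is chosen, its *At least intermediate* (1 or more) and *Poor* (3 or more) categories overlap as written. Make them mutually exclusive: observed score 1-2 against 3 or more.
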